### 5.1.2 Justification of the Study Design

QHD04 study will describe the safety of the 3 different dosages of QIV-HD in children 6 months to 17 years of age. The study will also describe the immunogenicity of the different dosages of QIV-HD compared to a unadjuvanted QIV-SD (Fluarix Quadrivalent, licensed in the US) in all stages of the study and compared to an adjuvanted TIV (FLUAD Pediatric, licensed in Canada) during Stage 4 after the highest acceptable dosage of QIV-HD is established. Both comparators will be obtained commercially and will be used according to the approved indication.

Given the different volumes in the 3 different dosages of the QIV-HD and the comparator vaccines, QHD04 will be a staged, modified double-blind study with an unblinded administrator used at each study site. The administrator will not be involved in any of the blinded study assessments (eg, safety).

Since this is the first time that the QIV-HD will be administered to the pediatric population, an ESDR will be performed for subjects 6 months to 8 years of age prior to dosage ascension (30, 45, and 60 µg HA/strain/dose).

Given the matured immune system in children 9 to 17 years of age, no ESDR will occur for subjects 9 to 17 years of age prior to dosage ascension. Subjects 9 to 17 years of age will be randomized to receive the 30 and 45 µg HA/strain/dose vaccines separately from subjects 9 to 17 years of age who receive the 60 µg HA/strain/dose formulation in order to maintain the randomization ratio across all age groups and thus allow for pooling of the 30, 45, and 60 µg HA/strain/dose formulations across all age groups as well.

The comparison of the QIV-HD that will be used in Stage 4 (highest dosage with acceptable safety) to the adjuvanted TIV will be an indicator in terms of expected vaccine efficacy since FLUAD Pediatric is the only licensed pediatric vaccine with studies evaluating both HAI immunogenicity and relative efficacy data.

### 5.1.3 Study Plan

The study plan is summarized in the [Table of Study Procedures](#).

#### *Vaccination*

All eligible subjects will be randomized to receive 1 or 2 doses of either QIV-HD, Fluarix® Quadrivalent (unadjuvanted QIV-SD), or FLUAD Pediatric® (adjuvanted TIV). The dosage of QIV-HD that is administered will depend on both the age of the subject and the stage at which he / she is enrolled.

- Subjects 9 to 17 years of age will receive 1 dose of the QIV-HD or the comparator vaccine on D0.
- Previously influenza vaccinated subjects 6 months to 8 years of age will receive 1 dose of the QIV-HD or the comparator vaccine on D0.
- Previously influenza unvaccinated subjects 6 months to 8 years of age will receive 2 doses of the QIV-HD or the comparator vaccine. Each dose will be administered 28 days apart (at D0 and D28).

Of note, the highest dosage with an acceptable safety review in prior stages will determine the dose evaluated in Stage 4.

An unblinded administrator at each site will administer the vaccine.

### ***Blood sampling***

Subjects will provide 2 or 3 blood samples, regardless of the stage of enrollment:

- Subjects 9 to 17 years of age will provide a pre-vaccination (baseline) blood sample at V01 (D0) and a post-vaccination blood sample at V03 (D28 [+7 days]) for HAI and SN testing.  
Note: Subjects 9 to 17 years of age are scheduled for 2 site visits. However, the second visit is designated as V03 to be consistent with the visits nomenclature of the 6 months to 8 years age groups.
- Previously influenza vaccinated subjects 6 months to 8 years of age will provide a pre-vaccination (baseline) blood sample at V01 (D0) and a post-vaccination blood sample at V03 (D28 [+7 days]) for HAI and SN testing.
- Previously influenza unvaccinated subjects 6 months to 8 years of age will provide a pre-vaccination (baseline) blood sample at V01 (D0) and a post-vaccination blood sample at V03 (D28 [+7 days]) and V05 (28 days after V03 [+7 days]) for HAI and SN testing.

Note: The blood sample will be taken prior to vaccination during any visit when a subject receives a vaccination.

### ***Collection of safety data***

All subjects will be observed for 30 minutes after vaccination, and any unsolicited systemic adverse events (AEs) occurring during that time will be recorded as immediate unsolicited systemic AEs in the case report book (CRB).

Solicited reactions will be collected up to 7 days after each vaccination, and unsolicited AEs will be collected up to D28 (V03) for subjects receiving 1 dose and up to D56 (V05) for subjects receiving 2 doses. Serious adverse events (SAEs) and adverse events of special interest (AESIs) will be collected throughout the study (D0 through approximately 6 months after the last vaccination). It is to be noted that AESIs will be captured as SAEs. These include new onset of Guillain-Barré syndrome (GBS), encephalitis / myelitis (including transverse myelitis), Bell's palsy, convulsions, optic neuritis, and brachial neuritis.

Subjects / parents / guardians will be asked to notify the site immediately about any potential SAEs (including AESIs) at any time during the study.

The study staff will contact subjects 9 to 17 years of age or the subjects' parents / guardians by phone at D8 (+2 days) post-vaccination to identify whether the subject experienced any SAEs not yet reported and will remind the subjects / subjects' parents / guardians to bring the completed diary card with them to V03 (D28 [+7 days]). The study staff will review the D0 to V03 safety data with subjects at V03.

Subjects 6 months to 8 years of age will return to the site at D8 (+3 days) after each vaccination. Staff will review the recorded solicited reactions and unsolicited AEs, and determine whether the subject experienced any SAEs and AESIs not yet reported. Staff will review the safety data with

subjects / subjects' parents / guardians at each visit. Staff will also remind the subjects / subjects' parents / guardians to bring the completed diary card with them to the subsequent visit.

The interactive response technology (IRT) system will be used to randomly assign subjects to a study product and to assign subject numbers in each of the groups.

Electronic data capture (EDC) will be used for the collection of data.

#### ***Review of safety data***

The study will be divided into 4 stages as described in [Section 5.1.1](#). An ESDR will be conducted for subjects 6 months to 8 years of age. The ESDR will occur following the collection of the safety data at V02 (approximately 8 days post-vaccination) of Stages 1, 2, and 3 by the SMT. Enrollment of subjects in the next stage will be initiated if the safety review results are satisfactory. The details of the safety reviews are described in [Section 5.1.6](#).

#### **5.1.4 Visit Procedures**

##### ***Visit 1 (Day 0): Inclusion, Randomization, Blood sample, and Vaccination – for all subjects***

###### **The Investigator or delegate will:**

- 1) Give the subject and / or subject's parent / guardian information about the study.
- 2) Obtain informed consent and assent (for subjects 7 to 17 years of age) and answer any questions to ensure that the subjects and/or subject's parent / guardian have been informed of all aspects of the study that are relevant to their decision to participate.
- 3) Date and sign the ICF (and assent form for subjects 7 to 17 years of age) after it has been signed and dated by the subject or subject's parent / guardian. Retain the original and give a signed copy to the subject or subject's parent / guardian.
- 4) Check all inclusion and exclusion criteria (see [Section 5.2.4](#) and [Section 5.2.5](#), respectively) through physical examination and medical interview of the subject and / or subject's parent / guardian. If the subject is not eligible, only the specific form entitled "Recruitment log" will state the subject identification, no CRB will be completed.
- 5) Collect relevant demographic information (eg, date of birth, sex, ethnicity, and race).
- 6) For females of childbearing potential, conduct a urine pregnancy test.
- 7) Obtain verbal information on medical history.
- 8) Obtain information on seasonal influenza vaccination and any influenza diagnosis as follows:
  - For previously influenza unvaccinated subjects, confirm that the subject has not been vaccinated with any seasonal influenza vaccine since birth and has never had a known influenza diagnosis.

Note: For the US sites, in following the Advisory Committee on Immunization Practices (ACIP) Guidelines, this study will consider subjects 6 months to 8 years of age who have never been vaccinated against influenza or who have not received at least 2 doses of seasonal influenza vaccine in a prior influenza season as "previously influenza unvaccinated subjects" when enrolling and thus these subjects will receive 2 doses of study vaccine at least 28 days apart. Subjects whose vaccination history is unknown will

also be considered as “previously influenza unvaccinated subjects” when enrolling and also receive 2 doses of study vaccine at least 28 days apart.

For the Canadian sites, in following the National Advisory Committee on Immunization (NACI) recommendations, this study will consider subjects 6 months to less than 24 months of age who have never been vaccinated against influenza in a prior influenza season as “previously influenza unvaccinated subjects” when enrolling and thus these subjects will receive 2 doses of study vaccine at least 28 days apart. Subjects who have received at least one dose of any influenza vaccine in the past will not be considered “previously influenza unvaccinated subjects”.

- For previously influenza vaccinated subjects, obtain the date (month and year) when the subject was last vaccinated with a seasonal influenza vaccination.  
**Note:** For the US sites, in following the ACIP Guidelines, this study will consider subjects 6 months to 8 years of age who have received at least 2 doses of seasonal influenza vaccine in prior influenza seasons as “previously influenza vaccinated subjects” when enrolling and thus these subjects will receive only 1 dose of study vaccine.

- 9) For subjects 6 to 12 months of age, obtain information on influenza vaccination during the mother’s pregnancy and breastfeeding routines, if any.
- 10) Collect any reportable concomitant medications (see [Section 6.7](#)).
- 11) Perform and document a targeted physical examination per standard site-specific immunization practices and record temperaturea in the source documents.
- 12) Call the IRT for assignment of the 12-digit subject number, randomization, and allocation of a dose number (see [Section 6.5](#)).
- 13) Draw approximately 5 mL of blood sample (The blood sampling should be performed before vaccination). Process the blood sample as specified in the “Management of Samples” section (see [Section 7](#)).

**Note:** If 5 mL of blood sample cannot be drawn, a volume less than 5 mL can be obtained.

**Note:** If the subject’s parent / guardian withdraws consent before blood sampling (before any invasive procedure has been performed), do not vaccinate the subject. The subject should be terminated from the study.

**Note:** If the attempt(s) to collect blood is (are) unsuccessful (3 attempts), then the subject is still to be included in the study and vaccinated.

The unblinded qualified study staff member will:

- 14) Administer the appropriate vaccine intramuscularly into the anterolateral muscle of the thigh or the deltoid muscle of the upper arm, as appropriate (the vaccine must be administered on the side opposite to that of the blood sampling).
- 15) Record the injection site / side / route / dose number and affix the detachable corresponding label in the source documents.

---

a Tympanic and temporal artery thermometer should not be used.

The Investigator or delegate will:

- 16) Keep the subject under medical surveillance for at least 30 minutes after the injection and report the occurrence or non-occurrence of any AE in the source documents.
- 17) Give the subject or subject's parent / guardian the diary card (DC) 1 to record any injection site reactions and systemic AEs, together with instructions for its completion, including explanations on the definition and use of intensity scales for collection of AEs.
- 18) Give the subject or subject's parent / guardian a ruler to measure the size of any injection site reaction, a thermometer for temperature measurement, and instructions on how to use them.
- 19) Remind the subject or subject's parent / guardian to bring back the DC1 when they return for V02. For subjects 9 to 17 years of age, schedule the D8 telephone call.
- 20) Remind the subject or subject's parent / guardian to promptly notify the site in case of an SAE/AESI that may occur at any time during the study.
- 21) Complete the relevant CRB forms for this visit.

***Telephone call (8 [+2] days after Visit 1): Collection of Safety Information – for subjects 9 to 17 years of age***

**Note:** If the telephone call falls on a weekend or a holiday, the telephone call may be scheduled on the next business day.

The Investigator or delegate will:

- 1) Record relevant information concerning the subject's health status on the telephone contact form. If an SAE occurred, follow the instructions in [Section 10](#) for reporting it.
- 2) Remind the subject or subject's parent / guardian to do the following:
  - Complete the remaining pages of the DC1 and bring the completed diary to V03 (D28 [+7 days]).
  - Notify the site in case of an SAE.

***Visit 2 (8 [+3] days after Visit 1): Collection of Safety Information – for subjects 6 months to 8 years of age***

**Note:** If Visit 2 falls on a weekend or a holiday, the visit may be scheduled on the next business day.

The Investigator or delegate will:

- 1) Review (for clarity, content, and completeness) the information in the DC1 with the subject or subject's parent / guardian and clarify with the subject or subject's parent / guardian, if required, any AEs, medications (see [Section 6.7](#)), or SAE that occurred since V01. If an SAE occurred, follow the instructions in [Section 10](#) for reporting it.
- 2) Record the D0 to D7 safety data in the CRB.
- 3) Remind the subject or subject's parent / guardian to do the following:
  - Complete the remaining pages of the DC1 and bring the completed diary to V03
  - Notify the site in case of an SAE.

***Visit 3 (28 [+7] days after Visit 1) – for subjects 9 to 17 years of age and for previously influenza vaccinated subjects 6 months to 8 years of age***

Note: Subjects 9 to 17 years of age are scheduled for 2 site visits. However, the second visit is designated as V03 to be consistent with the visit nomenclature of the 6 months to 8 years age groups.

**The Investigator or delegate will:**

- 1) Review (for clarity, content, and completeness) and collect the DC1 information with the parent / guardian and clarify with the parent / guardian if required any AEs, medications (see [Section 6.7](#)), or SAE that occurred since the telephone call (for subjects 9 to 17 years of age) or V02 (for previously vaccinated subjects 6 months to 8 years of age). If an SAE occurred, follow the instructions in [Section 10](#) for reporting it.

- 2) Draw approximately 5 mL of blood sample. Process the blood sample as specified in the “Management of Samples” section (see [Section 7](#)).

**Note:** If 5 mL of blood sample cannot be drawn, a volume less than 5 mL can be obtained.

**Note:** If the attempt(s) to collect blood is (are) unsuccessful (3 attempts), the parent / guardian should be given the opportunity to bring his / her child to the study site for another attempt within the visit window. If a blood sample cannot be obtained, the reason will be recorded in the blood sampling page of the CRB. In this case, the subject will be followed for safety in the study.

- 3) Provide the subject / parent / guardian with a memory aid (MA) and review the directions for its use.
- 4) Remind the subject / parent / guardian to promptly notify the site in case of an SAE that may occur at any time during the study.
- 5) Schedule the 6-month safety follow-up phone call
- 6) Record all applicable information obtained into the CRB
- 7) Complete the termination record of the CRB.

***Visit 3 (28 [+7] days after Visit 1) – for previously influenza unvaccinated subjects 6 months to 8 years of age***

**The Investigator or delegate will:**

- 1) Review (for clarity, content, and completeness) and collect the DC1 information with the parent / guardian and clarify with the parent / guardian if required any AEs, medications (see [Section 6.7](#)), or SAE that occurred since V02. If an SAE occurred, follow the instructions in [Section 10](#) for reporting it.

- 2) Conduct a targeted physical examination, if necessary.

- 3) Review temporary and definitive contraindications to vaccination.

- 4) Draw approximately 5 mL of blood sample (The blood sampling should be performed before vaccination). Process the blood sample as specified in the “Management of Samples” section (see [Section 7](#)).

**Note:** If 5 mL of blood sample cannot be drawn, a volume less than 5 mL can be obtained.

**Note:** If the attempt(s) to collect blood is (are) unsuccessful (3 attempts), the parent / guardian should be given the opportunity to bring his / her child to the study site for another attempt within the visit window. If a blood sample cannot be obtained, the reason will be recorded in the blood sampling page of the CRB. In this case, the subject will remain in the study and should be vaccinated after all the attempts to collect blood are complete.

The unblinded qualified study staff member will:

- 5) Call the IRT to obtain a unique dose number
- 6) Administer the appropriate vaccine intramuscularly into the anterolateral muscle of the thigh or the deltoid muscle of the upper arm, as appropriate (the vaccine must be administered on the side opposite to that of the blood sampling).
- 7) Record the injection site / side / route / dose number in the source documents and affix the detachable corresponding label in the source document.

The Investigator or delegate will:

- 8) Keep the subject under medical surveillance for at least 30 minutes after the injection and report the occurrence or non-occurrence of any AE in the source documents.
- 9) Give the subject / parent / guardian the DC2 to record any injection site reactions and systemic AEs, together with instructions for its completion, including explanations on the definition and use of intensity scales for collection of AEs.
- 10) Remind the subject / parent / guardian to bring back the DC2 when they return for V04.
- 11) Remind the subject / parent / guardian to promptly notify the site in case of an SAE that may occur at any time during the study.
- 12) Complete the relevant CRB forms for this visit.

***Visit 4 (8 [+3] days after Visit 3) – for previously influenza unvaccinated subjects 6 months to 8 years of age***

The Investigator or delegate will:

- 1) Review (for clarity, content, and completeness) the information in the DC2 with the subject / parent / guardian and clarify with the parent / guardian, if required, any AEs, medications (see [Section 6.7](#)), or SAE that occurred since V03. If an SAE occurred, follow the instructions in [Section 10](#) for reporting it.
- 2) Record the D28-D35 safety data in the CRB.
- 3) Remind the subject / parent / guardian to do the following:
  - Complete the remaining pages of the DC2 and bring them to V05
  - Notify the site in case of an SAE.

***Visit 5 (28 [+7] days after Visit 3) – for previously influenza unvaccinated subjects 6 months to 8 years of age***

The Investigator or delegate will:

- 1) Review (for clarity, content, and completeness) and collect the DC2 information with the parent / guardian and clarify with the subject / parent / guardian if required any AEs, medications (see [Section 6.7](#)), or SAE that occurred since V04. If an SAE occurred, follow the instructions in [Section 10](#) for reporting it.
- 2) Draw approximately 5 mL of blood sample. Process the blood sample as specified in the “Management of Samples” section (see [Section 7](#)).  
**Note:** If 5 mL of blood sample cannot be drawn, a volume less than 5 mL can be obtained.  
**Note:** If the attempt(s) to collect blood is (are) unsuccessful (3 attempts), the parent / guardian should be given the opportunity to bring his / her child to the study site for another attempt within the visit window. If a blood sample cannot be obtained, the reason will be recorded in the blood sampling page of the CRB. In this case, the subject will remain in the study.
- 3) Provide the subject / parent / guardian with a MA and review the directions for its use.
- 4) Remind the subject / parent / guardian to promptly notify the site in case of an SAE that may occur at any time during the study.
- 5) Schedule the 6-month safety follow-up phone call
- 6) Record all applicable information obtained into the CRB
- 7) Complete the termination record of the CRB.

***Safety Follow-up Telephone Call – approximately 6 months after the last vaccination:  
Collection of SAEs***

- 1) Inquire about new occurrences of SAEs and perform follow-up on SAEs. If an SAE has occurred, inquire if the subject has received any vaccinations or other medications since the last contact.
- 2) Explain that this will be the last contact with the site for this study (except for subjects with SAEs that need further follow-up, as stated below).

If the first contact attempt to complete the last telephone call is unsuccessful, at least 2 separate additional attempts, conducted on different days, should be made to contact these subjects. All attempts must be documented in the subject’s source notes. If, after at least 3 documented attempts, contact cannot be established, the subject should be classified as Lost to Follow-Up (see [Section 5.2.9](#) for further details).

The exceptions for the final phone calls are:

- Subjects who voluntarily withdrew
- Subjects who have been previously classified as lost to follow-up

***Follow-up of subjects with Related AEs or with AEs That Led to Study/Vaccination Discontinuation:***

A subject who experiences an AE (whether serious or non-serious) during the study must be followed until the condition resolves, becomes stable, or becomes chronic (even after the end of the subject’s participation in the study) if *either* of the following is true:

- The AE is considered by the Investigator to be related to the product administered.
- The AE caused the discontinuation of the subject from the study or from vaccination.

### 5.1.5 Planned Study Calendar

The following dates are approximate. The actual dates may differ as, for example, the study will not start until all the appropriate regulatory and ethical approvals have been obtained.

Planned study period - FVFS (first visit, first subject) to LCLS (last contact, last subject; phone call at the end of the 6-months follow up period): 10 October 2018 – 15 October 2019

Planned inclusion period - FVFS to FVLS (first visit, last subject):

- Stage 1a: 10 October 2018 – 19 October 2018
- Stage 2: 05 November 2018 – 09 November 2018
- Stage 3: 29 November 2018 – 10 December 2018
- Stage 4: 03 January 2019 – 28 February 2019

Planned study period (active phase) – FVFS to LVLS (last visit, last subject):

- Stage 1: 10 October 2018 – 21 November 2018
- Stage 2: 05 November 2018 – 11 January 2019
- Stage 3: 29 November 2018 – 11 February 2019
- Stage 4: 03 January 2019 – 02 May 2019

Planned end of study (LCLS; phone call at the end of the 6-months follow up period): 15 October 2019

Planned date of final clinical study report: 05 March 2020

### 5.1.6 Early Safety Data Review

The safety of the investigational product will be continuously monitored by the Sponsor. ESDRs will be performed, the goal of which is to allow for a cautious, stepwise approach to vaccine administration. A stepwise dosage ascension approach will be applied to subjects in age group 5 to 8 years (30 µg, 45 µg, and 60 µg HA/strain/dose). A stepwise age de-escalation vaccination approach will be taken for subjects in age group 36 months to < 5 years of age, with an ESDR prior to vaccinating subjects in the age group 6 to < 36 months of age as well as stepwise dosage ascension. The ESDR will be performed following V02 in subjects 6 months to 8 years of age (refer to [Figure 5.1](#) and [Figure 5.2](#)).

The ESDRs for this study are planned after the 6 months to 8 years age groups in each stage have been vaccinated and have provided safety data for Days 0 to 7 post-vaccination, using the data collection methods described in the protocol. ESDR will not be performed for subjects 9 to 17 years of age.

---

a Enrollment of subjects 9 to 17 years of age may be extended

During each ESDR, enrollment of subjects will be paused. However, already enrolled subjects 6 months to 8 years of age who require 2 vaccinations because of their previous vaccination status will receive their second dose at D28 as scheduled, which may be prior to the ESDR. Following a satisfactory safety review, enrollment of subjects will resume for the subsequent or appropriate Stage as described in [Figure 5.1](#) and [Figure 5.2](#). The study visits according to the [Table of Study Procedures](#) will continue to be followed for enrolled subjects within each active Stage (ie, subjects will complete their scheduled visits).

The safety data collected will be entered into the CRBs and summarized by the Sponsor in a blinded manner. A review will be performed by the Sponsor during the SMT meetings. It is understood that this review is based on preliminary data that have not been subject to validation and database lock. (The usual and ongoing process of monitoring safety signals outside of those specified in the protocol-defined early interim safety analysis will continue unchanged.)

The following safety parameters will be assessed as part of the early safety review:

- Immediate reactions
- Solicited injection site and systemic reactions
- Unsolicited AEs
- SAEs (including AESIs)

Enrollment will be paused during the review, and the data will be examined for the following occurrences:

- An SAE (including AESIs) considered as related to the vaccination by the Investigator and Sponsor
- > 10% of subjects experiencing Grade 3 fever within 7 days after vaccination

If any of the above criteria are met, a decision will be made as to whether enrollment in the study will be allowed to resume.

Case unblinding may be performed if necessary.

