- Previously influenza vaccinated and unvaccinated subjects 36 months to < 5 years of age (Group 1) will be randomized to receive either QIV-HD at 30 µg HA/strain/dose or the unadjuvanted QIV-SD. Based on the early safety data review, the study will either stop (Group 1 does not pass safety review) or continue into Stage 2 .
- Previously influenza vaccinated and unvaccinated subjects 5 to 8 years of age (Group 9), will be randomized to receive either QIV-HD at 30 µg HA/strain/dose or the unadjuvanted QIV-SD. Based on the early safety data review, the enrollment of this age group will either stop (Group 9 does not pass safety review) or continue into Stage 2.
- Previously influenza vaccinated and unvaccinated subjects 9 to 17 years of age (hereafter will be referred to as subjects 9 to 17 years of age) will be divided into 2 groups (Group 12 and Group 13). Group 12 will be enrolled first and will be randomized to receive either QIV-HD at 30 µg, or 45 µg HA/strain/dose or the unadjuvanted QIV-SD. Once the enrollment of Group 12 is complete, subjects in Group 13 will be randomized to receive either QIV-HD at 60 µg or the unadjuvanted QIV-SD. Subjects 9 to 17 years of age will not undergo an ESDR.

Stage 2 will include 3 age groups (6 to < 36 months, 36 months to < 5 years, and 5 to 8 years) and will be conducted in the US:

- Previously influenza vaccinated and unvaccinated subjects 36 months to < 5 years of age (Group 2) will receive either QIV-HD at 45 µg HA/strain/dose or the unadjuvanted QIV-SD and previously influenza vaccinated and unvaccinated subjects 6 to < 36 months of age (Group 3) will receive either QIV-HD at 30 µg HA/strain/dose or the unadjuvanted QIV-SD. Based on the early safety data review, the study will either stop (Group 3 does not pass safety review), continue and skip to Stage 4 (Group 2 does not pass safety review), or continue to Stage 3 (Group 2 and Group 3 both pass the safety review).
- Previously influenza vaccinated and unvaccinated subjects 5 to 8 years of age (Group 10), will be randomized to receive either QIV-HD at 45 µg HA/strain/dose or the unadjuvanted QIV-SD. Based on the early safety data review, the enrollment of this age group will either stop (Group 10 does not pass safety review) or continue into Stage 3.

Stage 3 will include 3 age groups (6 to < 36 months, 36 months to < 5 years, and 5 to 8 years) and will be conducted in the US:

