- Previously influenza vaccinated and unvaccinated subjects 36 months to < 5 years of age (Group 4) will receive either QIV-HD at 60 µg HA/strain/dose or the unadjuvanted QIV-SD; and previously influenza vaccinated and unvaccinated subjects 6 to < 36 months of age (Group 5) will receive either QIV-HD at 45 µg HA/strain/dose or the unadjuvanted QIV-SD. Based on the early safety data review, the highest dosage with an acceptable safety review will be determined and used in Stage 4.
- Previously influenza vaccinated and unvaccinated subjects 5 to 8 years of age (Group 11) will be randomized to receive either QIV-HD at 60 µg HA/strain/dose or the unadjuvanted QIV-SD.

Stage 4 will include 2 age groups (6 to < 36 months and 6 to < 24 months) and will be conducted in the US (subjects 6 to < 36 months) and Canada (subjects 6 to < 24 months):

- Previously influenza unvaccinated subjects 6 to < 36 months of age (Group 6) and previously influenza vaccinated subjects 6 to < 36 months of age (Group 7) will be randomized to receive either the highest dosage of QIV-HD with an acceptable safety review or the unadjuvanted QIV-SD.
- Previously influenza unvaccinated subjects 6 to < 24 months of age (Group 8) will receive either the highest dosage of QIV-HD with an acceptable safety review or the adjuvanted TIV.

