#### 5.2.7.1 Temporary Contraindications

Should a subject experience one of the conditions listed below, the Investigator will postpone further vaccination until the condition is resolved. Postponement must still be within the timeframe for vaccination indicated in the [Table of Study Procedures](#).

- Febrile illness (temperature  $\geq 38.0^{\circ}\text{C}$  [ $\geq 100.4^{\circ}\text{F}$ ]) or moderate or severe acute illness / infection on the day of vaccination, according to Investigator judgment.

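### In Groups 2, 4, 5, 9 and 10, no rule ties a child's pending second dose to the group's early safety review result, while the default is to give it on schedule

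*Protocol*

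**What the plan says.** Protocol 5.1.6 lists two occurrences to look for: a related SAE, and Grade 3 fever within 7 days in more than 10% of subjects. If either is found, "a decision will be made as to whether enrollment in the study will be allowed to resume". The synopsis and SAP 5.6 say the same.

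Protocol 5.1.1 gives the result by group:

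- Group 2 (45 µg, 36 months to < 5 years): the study will "continue and skip to Stage 4 (Group 2 does not pass safety review").
- Group 9 (30 µg, 5 to 8 years): "the enrollment of this age group will either stop (Group 9 does not pass safety review").
- Group 10 (45 µg, 5 to 8 years): "the enrollment of this age group will either stop (Group 10 does not pass safety review").
- Groups 4 and 5 (60 µg and 45 µg, Stage 3): "the highest dosage with an acceptable safety review will be determined and used in Stage 4".
- Groups 1 and 3: on a non-pass, the study as a whole stops.

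On second doses, 5.1.6 says that two-dose children already enrolled "will receive their second dose at D28 as scheduled, which may be prior to the ESDR". It adds that enrolled subjects within each active Stage complete their scheduled visits. The synopsis and SAP 5.6 repeat this.

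**The concern.** Protocol 5.1.2 describes this as the first use of QIV-HD in children, and 5.1.6 gives the aim of the ESDR as caution in administering the vaccine, not only in enrolling. For five groups, a dosage that has not passed its review has a stated effect on children not yet enrolled or on a later stage. It has none on children who have had that dosage once and are due it again. Followed literally, the text would give them a second injection of a dosage that had just failed.

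The individual contraindications in 5.2.7.2 do not close this gap. D07 needs the child's own related SAE, and D06 needs the Investigator's judgment about that child. A group can meet the fever criterion with no SAE at all. Its other children then meet no listed contraindication unless D06 is used. No ESDR is planned after dose 2, so this review is the only planned group-level check before re-exposure.

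**Working it through.** **1. Group sizes.** From Protocol 12.5: six groups of 40, one of 90, five of 60 and one of 70 give 240 + 90 + 300 + 70 = 700, the planned total. The five groups at issue hold 4 × 40 + 90 = 250 children, of whom 4 × 30 + 45 = 165 receive QIV-HD.

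**2. Are second doses still pending when the review ends?** Inputs are the inclusion dates in Protocol 5.1.5, which are approximate, and the windows in the Table of Study Procedures: V02 at D8 (+3) and V03 at D28 (+7). Last V02 = last inclusion + 11. First dose 2 = first inclusion + 28. The opening of the next stage stands in for the end of review.

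| | Stage 1 (Group 9) | Stage 2 (Groups 2, 10) | Stage 3 (Groups 4, 5) |
|---|---|---|---|
| Inclusion | 10–19 Oct | 5–9 Nov | 29 Nov–10 Dec |
| Last V02 (D11) | 30 Oct | 20 Nov | 21 Dec |
| Next stage opens | 5 Nov | 29 Nov | 3 Jan |
| First D28 | 7 Nov | 3 Dec | 27 Dec |
| Last V02 to first D28 | 8 days | 13 days | 6 days |
| Last V02 to next opening | 6 days | 9 days | 13 days |
| Inclusion days with D28 on or after next opening | 10 of 10 | 5 of 5 | 5 of 12 |

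If every V02 is on D8, the gaps from last V02 to first D28 are 11, 16 and 9 days. The SAP gives the V02 window as +2 days, which falls between the two cases.

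The Stage 1 active-phase end in 5.1.5 (21 Nov) is not used. It precedes the earliest possible Stage 1 D56, 10 Oct + 56 days = 5 Dec.

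**3. How late can the decision come without an extra visit?** First inclusion + 35 gives 14 Nov, 10 Dec and 3 Jan. These are 15, 20 and 13 days after the last V02. In Stage 3 that date equals the planned opening of Stage 4, so there is no slack.

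**4. How many children?** The share needing two doses is not stated. Assuming 25%, 50% or 75%:

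- QIV-HD arm of 30 (Groups 2, 5, 9, 10): 7.5, 15 or 22.5, so about 8, 15 or 23.
- QIV-HD arm of 45 (Group 4): 11.25, 22.5 or 33.75, so about 11, 23 or 34.

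**5. The fever criterion.** If the 10% is applied per group, which the text does not specify, it is met at 5 of 40 children (12.5%), or 10 of 90 in Group 4 (11.1%).

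**The case against.** The strongest reply is that the power to act already exists and sits with the same party. The Sponsor's SMT runs the ESDR, and "The safety of the investigational product will be continuously monitored by the Sponsor". The Sponsor may withdraw a subject for safety concerns (5.2.8), and the study may be discontinued (5.5) or modified (10.4). All of that stands. These powers permit action on dose 2, but none requires it to be considered with the group's result.

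Second, the plan did think about these children. Keeping them on schedule during the review is a disclosed choice and a defensible one. A reader might therefore infer that the plan is silent on second doses, and the documents do not support that. Section 5.1.6 gives a default, and the sentence on completing visits extends it to enrolled subjects in each active Stage. Whether a Stage whose group has failed is still active is not defined. The gap is narrower than silence: nothing links that default to a failed review.

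Third, Protocol 1.3.2 says systemic reactions mostly affect people not previously exposed to the antigens, so fever after dose 1 need not recur after dose 2. That is a reason the SMT might release dose 2. It does not remove the need to decide.

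Fourth, one might infer that every pending injection must be frozen as soon as a criterion is met. Section 5.1.6 makes a met criterion a prompt for a decision, not a failure. An automatic freeze could also delay licensed QIV-SD for children in influenza season because of one event. Whether to hold is a benefit-risk judgment for the SMT.

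Finally, 5.1.6 refers to Figures 5.1 and 5.2 for the path after review. Neither could be read, so the point covers the text only.

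**Conclusion.** The point holds in this limited form. In the visible text, a met criterion or a non-pass in Groups 2, 4, 5, 9 or 10 has consequences only for enrollment, staging or the Stage 4 dosage. The stated default for children already enrolled is dose 2 at D28, and no rule connects the two.

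Two wider readings are not supported. The Sponsor is not powerless to stop dose 2. Nor does the point extend to Groups 1 and 3, where stopping the study most naturally includes dosing; at most a clarifying word is useful there.

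The exposure is roughly 8 to 34 pending QIV-HD second doses per failed group. That rests on an assumed two-dose share of 25% to 75% and on full enrollment. The timing rests on approximate dates and on the next stage's opening as the end of review. On that basis the decision can normally come before dose 2 in Stages 1 and 2, and for part of Stage 3. Confidence is moderate because the figures are missing and the general powers are real.

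**What to change.** In Protocol 5.1.6, the synopsis and SAP 5.6, widen the decision sentence along these lines: *when a criterion is met, or a group does not pass its review, the SMT decides both whether enrollment resumes and whether pending second doses of that QIV-HD dosage are given to children already enrolled.* Then add:

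- Any SMT stop is applied through the IRT call already made at V03 (5.1.4).
- QIV-SD recipients are released where possible, for example by the case unblinding that 5.1.6 allows.
- Children not given dose 2 are followed as in 5.2.7.2.
- A hold while the SMT deliberates is at its discretion; V03 can be booked later within its +7-day window meanwhile.
- The plan states whether a dose released after D35 may still be given. For temporary contraindications, 5.2.7.1 says "Postponement must still be within the timeframe for vaccination indicated in the" Table of Study Procedures, and nothing covers a hold by the SMT.

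The wording that dose 2 may precede the ESDR can stay, for late reviews and early Stage 3 inclusions.

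The cost is one sentence in three places and an IRT setting. No visit is added if the SMT decides by 14 Nov, 10 Dec or 3 Jan for Stages 1, 2 and 3 and V03 is booked accordingly. A dose released after V03 has taken place needs an extra visit and re-timed V04 and V05. A few children may get dose 2 late or not at all, and those who miss it fall outside the immunogenicity analysis set (Protocol 12.2.1, SAP 5.2.1).
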